8.3.2 Serology

Sera are tested for neutralizing antibody to RV16 and RV39 by a standard microtiter assay [33]. In addition to neutralizing antibodies, specific IgG and IgA antibodies directed against RV-16 and RV-39 capsid proteins, VP1 and VP2, will be measured in serum by antigen binding radioimmunoassay.

8.3.3 Other Laboratory Evaluations

HLA-DRB1 typing will be performed on whole blood DNA specimens obtained on subjects who meet criteria for RV challenge in order to select the relevant MHCII/RV peptide tetramer for T-cell phenotyping studies.

8.3.4 Special Assays or Procedures

At specified time points, PBMC specimens will be collected in order to perform high-dimensional immunophenotyping of circulating T cells and other immune cell types by mass cytometry. In addition, gene expression profiling of discrete T-cell subtypes will be performed using standard microarrays or single-cell analytical platforms (BioMark, Fluidigm).

Screening lab studies (Hgb and IgE) and the respiratory virus PCR will be done in the Clinical Laboratory of the UVA Medical Center. Specimens will be shipped to the laboratory using standard hospital procedures.

For details of laboratory evaluations, please refer to the Manual of Procedures (MOP), which contains the following standard operating procedures (SOPs):

1. Collection of whole blood for serum
2. Microtiter screening neutralization assay
3. RV isolation in cell culture
4. Quantitative RV cultures
5. RV typing neutralization assay
6. qPCR for RV
7. Serum IgG and IgA binding assays
8. DNA Isolation and HLA typing from whole blood.
9. PBMC isolation and cryopreservation
10. PBMC specimen thawing
11. Staining PBMCs with tetramers and antibodies
12. Analysis of samples by multi-color flow cytometry
13. Staining PBMCs for mass cytometry analysis (protocol 1)
14. Staining PBMCs for mass cytometry analysis (protocol 2)
15. Analysis of samples by mass cytometry
16. Single-cell gene expression profiling
17. Single-cell gene expression profiling (Fluidigm)
18. Gene expression profiling using standard microarrays
19. Multiplex cytokine assay for cytokines in nasal lavage fluid

8.3.5 Specimen Preparation, Handling, and Shipping

8.3.5.1 Instructions for Specimen Preparation, Handling, and Storage

All specimen collection and processing will be done in the research laboratories of the PIs using established procedures documented in the laboratory manuals of the respective laboratories (see MOP for details). Specimens will be stored at appropriate temperatures in monitored freezers. Consent for future use of the specimens will be obtained. All specimens will be identified by study number, date, and specimen type, and linked to the DCF and study database.

8.3.6 Specimen Shipment

DNA specimens may be shipped for HLA typing services to external sites (listed in the MOP). Additionally, assay plates containing cDNA specimens may be shipped for single-cell gene expression profiling (see MOP for details).

9 ASSESSMENT OF SAFETY

9.1 Methods and Timing for Assessing, Recording, and Analyzing Adverse Events and Serious Adverse Events

9.1.1 Adverse Event Definition

ICH E6 defines an AE as any untoward medical occurrence in a patient or clinical investigation subject who was administered a pharmaceutical product, regardless of its causal relationship to the study treatment. FDA defines an AE as any untoward medical occurrence associated with the use of a drug in humans, whether or not considered drug related.

An AE may be an unfavorable and unintended sign, symptom, syndrome, or illness that develops or worsens during the clinical study. Clinically relevant abnormal results of diagnostic procedures including abnormal laboratory findings (e.g., requiring unscheduled diagnostic procedures or treatment measures, or resulting in withdrawal from the study) are considered to be AEs. Any medical condition that is present at the time that the subject is screened will be considered as baseline and not reported as an AE. However, worsening of pre-existing medical condition will be recorded as an AE.

For the purposes of this study using experimental RV infection, physical signs and symptoms that are expected to be associated with the common cold and occur in the seven days after virus challenge should not be reported as AEs. The following physical signs and symptoms are expected to be associated with the common cold: nasal obstruction (nasal stuffiness), coryza (runny nose), sore throat, cough, sneezing, headache, chills, and malaise. If these symptoms are worsening beyond seven days after virus challenge they will be recorded as AEs. All other untoward medical occurrences during the study will be recorded as adverse events (such as fever, bronchospasm, asthma, otitis media, bronchitis and/or sinusitis).

9.1.2 Serious Adverse Event Definition

A Serious Adverse Event (SAE) or Serious Adverse Drug Reaction (SADR) is any Adverse Event (AE) that meets at least one of the following criteria:

1. Death.
2. Life-threatening adverse event;*
3. Inpatient hospitalization or prolongation of an existing hospitalization (see below).
4. Persistent or significant disability or incapacity or substantial disruption of the ability to conduct normal life function (see below).
5. Is a congenital anomaly or birth defect.
6. Important medical events **

*Life-threatening refers to immediate risk of death as the event occurred per the reporter. A life-threatening experience does not include an experience that had it occurred in a more severe form might have caused death, but as it actually occurred, did not create an immediate risk of

death. For example, hepatitis that resolved without evidence of hepatic failure would not be considered life-threatening, even though hepatitis of a more severe nature can be fatal. Similarly, an allergic reaction resulting in angioedema of the face would not be life-threatening, even though angioedema of the larynx, allergic bronchospasm, or anaphylaxis can be fatal.

**Important medical events that may not result in death, be life-threatening, or require hospitalization may be considered SAEs when, based on appropriate medical judgment, they may jeopardize the subject and may require medical or surgical intervention to prevent one of the outcomes listed in this definition. Examples of such events include allergic bronchospasm requiring intensive treatment in an emergency room or at home, blood dyscrasias or convulsions that do not result in hospitalization, or development of drug dependency or drug abuse.

Hospitalization is official admission to a hospital. Hospitalization or prolongation of a hospitalization constitutes criteria for an AE to be serious; however, it is not in itself considered a SAE. In absence of an AE, a hospitalization or prolongation of a hospitalization should not be reported as a SAE. This is the case in the following situations:

- The hospitalization or prolongation of hospitalization is needed for a procedure required by the protocol.
- The hospitalization or prolongation of hospitalization is part of a routine procedure followed by the center (e.g., stent removal after surgery). This should be recorded in the study file.

In addition, hospitalization, for a pre-existing condition that has not worsened, does not constitute an SAE.

Disability is defined as a substantial disruption in a person's ability to conduct normal life functions.

If there is any doubt about whether the information constitutes a SAE, the information is treated as a SAE.

9.1.3 Assessment and Reporting of Adverse Events:

9.1.3.1 Recording of Adverse Events

All AEs should be captured on the appropriate DCF. All AEs occurring while on study must be documented appropriately regardless of relationship, severity or seriousness criteria. All AEs will be followed to adequate resolution or stabilization. All AEs must be graded for severity and relationship to study product.

All volunteers will be specifically asked about any unexpected events at each study visit. All volunteers will be instructed to contact the study site if they experience any unexpected symptoms during the time they are in the study (from day 0 - day 63 for each challenge cohort). At the final study visit (day 63 for each challenge cohort), volunteers will be asked if they have

had any unusual symptoms or problems during the study. All positive responses will be recorded. Medically significant responses will be followed until the symptom/problem is resolved or judged unrelated to the study and the subject has been referred for appropriate care.

9.1.3.2 Severity

The severity of AEs will be graded on a three–point scale as described below as assessed by the volunteer and reported in detail as indicated on the DCF.

- **Mild** - Barely noticeable, does not interfere with daily activity,
- **Moderate** - Noticeable, but does not prevent daily activity,
- **Severe** - Interferes or prevents daily activity

Changes in the severity of an AE should be documented to allow an assessment of the duration of the event at each level of intensity to be performed. AEs characterized as intermittent require documentation of onset and duration of each episode.

9.1.3.3 Relationship to Study Intervention

All AEs must be graded for severity and relationship to study intervention. The investigator's assessment of an AE's relationship to study is part of the documentation process, but it is not a factor in determining what is or is not reported in this study. If there is any doubt as to whether a clinical observation is an AE, the event should be reported. The relationship to study must be assessed for AEs using the terms: related or not related. In a clinical trial, the study product must always be suspect. To help assess, the following guidelines are used:

- **Related:** There is a reasonable possibility that the study caused the adverse event. Reasonable possibility means that there is evidence to suggest a causal relationship between the study product and the adverse event. All causality relationship of probably not related, possibly related, probably related, and definitely related will be considered related regardless of form of documentation.
- **Not Related:** The event can be readily explained by other factors such as the subject's underlying medical condition, concomitant therapy, or accident, and no temporal relationship exists between the study drug and the event.

9.1.3.4 Type and Duration of Follow-up of Subjects after Adverse Events

Adverse events requiring medical intervention will be followed until the symptom/problem is resolved or the subject is considered stable. Subjects who experience AEs judged unrelated to the study will be referred for appropriate care as needed.

9.1.4 Assessment and Reporting of Serious Adverse Events

Any SAE occurring in a subject after Day 0 in each challenge cohort until Day 28 of the cohort must be reported. Any AE should be recorded on the appropriate DCF.

Unexpected SAEs that are fatal or life-threatening must be filed as soon as possible with the Ethics Committee as soon as possible but not later than 7 calendar days after first knowledge, followed by as complete a report as possible within 8 additional calendar days.

Unexpected SAEs that are not fatal or life-threatening must be filed as soon as possible but no later than 15 calendar days after first knowledge.

AEs will be followed until resolution even if this extends beyond the study-reporting period. Resolution of an AE is defined as the return to pretreatment status or stabilization of the condition with the expectation that it will remain chronic.

All SAEs will be:

- recorded on the appropriate SAE DCF
- followed through resolution by a study clinician
- reviewed and evaluated by a study clinician

Any AE that meets a protocol-defined serious criterion must be submitted immediately (within 24 hours of site awareness) on an SAE form to the DMID Pharmacovigilance Group, at the following address:

**DMID Pharmacovigilance Group
Clinical Research Operations and Management Support (CROMS)
[name]
Bethesda, MD 20817, USA
SAE Hot Line: [name] (US) or [name] (outside US)
SAE FAX [contact] (US) or [name] (outside US)
SAE Email Address: [contact]**

Other supporting documentation of the event may be requested by the DMID Pharmacovigilance Group and should be provided as soon as possible.

The DMID Medical Monitor and Clinical Protocol Manager will be notified of the SAE by the DMID Pharmacovigilance Group. The DMID Medical Monitor will review and assess the SAE for regulatory reporting and potential impact on study subject safety and protocol conduct.

At any time after completion of the study, if the investigator becomes aware of an SAE that is suspected to be related to study product, the investigator will report the event to the DMID Pharmacovigilance Group.

9.1.5 Reporting Plan for Serious Adverse Events, Unanticipated Problems, Protocol Deviations and Data Breaches

AEs will be reported to the UVA Human Investigations Committee for review as follows.

Type of Event	To whom will it be reported:	Time Frame for Reporting	How reported?
Any internal event resulting in death that is deemed DEFINITELY related to (caused by) study participation	IRB-HSR Medical Monitor	Within 24 hours	IRB Online and phone call www.irb.virginia.edu/
Internal, Serious, Unexpected adverse event	IRB-HSR Medical Monitor	Within 7 calendar days from the time the study team received knowledge of the event.	IRB Online www.irb.virginia.edu/
Unanticipated Problems that are not adverse events or protocol violations This would include a Data Breach.	IRB-HSR Medical Monitor	Within 7 calendar days from the time the study team received knowledge of the event.	Unanticipated Problem report form. http://www.virginia.edu/vprgs/irb/HSR_docs/Forms/Reporting_Requirements-Unanticipated_Problems.doc)
Protocol Violations/Noncompliance The IRB-HSR only requires that MAJOR violations be reported.	IRB-HSR Medical Monitor DMID	Within 7 calendar days from the time the study team received knowledge of the event.	Protocol Violation, Noncompliance and Enrollment Exception Reporting Form http://www.virginia.edu/vprgs/irb/hsr_for_ms.html
Data Breach	The UVA Corporate Compliance and Privacy Office Medical Monitor ITC: if breach involves electronic data UVA Police if breach includes such things as stolen computers.	As soon as possible and no later than 24 hours from the time the incident is identified. As soon as possible and no later than 24 hours from the time the incident is identified. IMMEDIATELY	UVA Corporate Compliance and Privacy Office [contact] ITC: Information Security Incident Reporting procedure, http://www.itc.virginia.edu/security/reporting.html [contact]

UVA PI HELD IND			
Life-threatening and/or fatal unexpected events related or possibly related to the use of the investigational agent.	FDA	Within 7 calendar days of the study team learning of the event	Form FDA 3500A (MedWatch) or narrative
Serious, unexpected and related or possibly related adverse events	FDA	Within 15 calendar days after the study team receives knowledge of the event	Form FDA 3500A (MedWatch) or narrative
All adverse events	FDA	Annually	IND annual report

9.1.6 Reporting of Pregnancy

Any pregnancy occurring between the screening and final visits for each cohort will be recorded and reported to the IRB, DMID and the Data Safety Monitoring Board (DSMB). No further study inoculations will be administered to pregnant subjects, but all study-mandated blood samples will be obtained and the subject will continue in follow-up for safety events. Pregnancies will be followed to pregnancy outcome pending the subject's permission.

9.2 Methods and Timing for Assessment of the Performance of the Human Rhinovirus Challenge Model

9.2.1 Historical performance of the challenge model

The experimental RV challenge model is a well-established model that has been used for the study of the pathogenesis and treatment of rhinovirus infections since the 1960s. There have been a number of variations on the model but the proposed procedures and evaluations in this protocol (described in section 8.2 above) and have been used by the PI for 35 years. Under these conditions, the expected infection rate for volunteers in the study is 85-90%. Mean symptom scores for the RV39 used in the study have typically been in the range of 14-18 with standard deviations of ± 13 . The mean total symptom scores for the RV16 was 20 ± 10 in the initial evaluation of the challenge pool.

The investigators are not aware of any previous rhinovirus challenge study that was discontinued because of unexpected risk to the volunteers in the study. In light of this experience, it is unlikely that events that would require stopping the study would occur.

9.2.2 Evaluation of viral infection

Infection performance will be monitored and assessed in two ways:

9.2.2.1 Back titration of the challenge pool

After each challenge a portion of the challenge inoculum is back titrated in cell culture to assure that viable virus is present at the approximate titer anticipated. The accuracy of the quantitative culture method is generally accepted to be $\pm 0.5 \log_{10}$ TCID₅₀/ml. Failure to detect virus in the back titration or detection of greater than $1 \log_{10}$ TCID₅₀/ml over the intended challenge inoculum will be reported to the Medical Monitor and DSMB.

9.2.2.2 Infection rate

Evaluation of viral infection to assess the performance of the model will be limited to the initial RV16 challenge in each cohort. The purpose of the study is to evaluate the effect of RV16 induced immunity on subsequent homotypic and heterotypic challenges so any change in the expected characteristics of the model will be more likely an effect of the experimental design than a change in the performance of the model. If the infection rate in the first challenge of any cohort is less than 75% this will be reported to the Medical Monitor and DSMB. Note that a decreased infection rate would potentially impact the data analysis and benefit of the study but would not pose a direct increased risk to the volunteers.

9.2.3 Evaluation of symptoms

Evaluation of symptoms to assess the performance of the model will be limited to the initial RV16 challenge in each cohort. The purpose of the study is to evaluate the effect of RV16 induced immunity on subsequent homotypic and heterotypic challenges so any change in the expected characteristics of the model in the re-challenged cohorts will be more likely an effect of the experimental design than a change in the performance of the model. Should the initial challenge result in an average total symptom score of <5 this will be reported to the Medical Monitor and the DSMB. Note that a decreased symptom burden would potentially impact parts of the data analysis and the benefit of the study but would not pose a direct increased risk to the volunteers.

Given the historical mean and standard deviation of the total symptom scores in the model, it would be an unexpected event if more than 10% of the volunteers in any cohort (initial challenge or re-challenge) had a total symptom score >40 . Should this occur we will report the event to the Medical Monitor and stop the study pending DSMB review.

9.2.4 Halting Rules

Each study cohort will be challenged with virus over one to two days so application of halting rules cannot be done during the cohort. The following halting rules will be applied and require DSMB review before proceeding to subsequent challenges.

- 9.2.4.1** More than 10% of volunteers in any cohort with a total symptom score >40
- 9.2.4.2** Any subject experiences type 1 hypersensitivity immediately after receiving the study product
- 9.2.4.3** Any SAE judged by the investigator to be related to the challenge virus infection.

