5.4 Treatment Assignment Procedures

5.4.1 Randomization Procedures

All volunteers will be challenged with RV16 at the first challenge. Randomization of subjects for challenge with either RV16 or RV39 at the second challenge will be done using GraphPad® software with randomization blocks of ten. The challenge pool used will be recorded on source documents and transferred to the data collection form (DCF).

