8.2.3 Assessment of infection and illness

Volunteers who have challenge virus detected in nasal lavage by culture or PCR on any of the Study Days 1-5 after virus challenge and/or have a four-fold rise in neutralizing antibody titer to the study virus are considered infected. Volunteers who have a positive culture for the challenge virus on any of the Study Days 1-5 after virus challenge are defined as “virus shedders” and the time from Day 0 to the first positive virus culture is defined as the “time to virus shedding”.

The total symptom score will be the sum of the symptom scores for all symptoms on Study Days 1-5. Infected volunteers who have a total symptom score of at least 6 and either at least 3 days of rhinorrhea or the subjective impression that they have had a cold will be defined as having a symptomatic infection.

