9.3.2 Data and Safety Monitoring Board (DSMB)

This clinical trial will utilize a DSMB, which will be comprised of an independent group of experts with experience with early phase clinical research studies. The primary responsibility of the DSMB is to monitor subject safety. The DSMB is external to DMID and composed of at least three voting members. The DSMB will consist of members with appropriate expertise to contribute to the interpretation of the data from this trial. Committee activities will be delineated in a DSMB charter that will delineate membership, responsibilities, and the scope and frequency of data reviews. The DSMB will operate on a conflict-free basis independently of the study team. DMID, the DSMB, the ISM or the PI may convene ad hoc meetings of the DSMB according to protocol criteria or if there are concerns that arise during the study. The DSMB will have access to unblinded data during its closed session, if applicable. After its assessment, the DSMB will recommend continuation, modification, or termination of the clinical trial.

The DSMB will conduct a review of all available safety data after each cohort has completed the day 8 study visit (7 days following the first study inoculation). The review will also include all available safety data on second inoculations accrued through the time of data freeze for the DSMB meeting and the DSMB will recommend continued enrollment of the remaining subjects, modification, or discontinuation of enrollment.

If any of the halting rules are met following the first or second study challenge, the study will not proceed with the remaining enrollment or study challenge without a review by and recommendation from the DSMB to proceed.

Upon completion of this review and receipt of the advice of the DSMB, DMID will determine if study entry or study dosing should be interrupted, or if study entry and study dosing may continue according to the protocol.

A final review of Safety data will be conducted after the study is completed. This review may be performed electronically if the DSMB Chair agrees.

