11.4.1 Safety Review

There are no specific safety outcome measures in this study. Reported AEs will be reviewed after each challenge cohort. Unexpected or serious events judged to be related to the virus challenge will be reviewed with the ISM, the DSMB and DMID before the next cohort is challenged.

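### The reason section 9.2.4 gives for not halting within a cohort does not fit immediate type 1 hypersensitivity, and section 9.3.2 leaves unclear whether dosing must stop

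*Combined protocol and SAP*

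**What the plan says.** Section 9.2.4 states that each cohort's inoculations are completed in one or two days, "so application of halting rules cannot be done during the cohort". It continues: "The following halting rules will be applied and require DSMB review before proceeding to subsequent challenges". Three rules follow:

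- 9.2.4.1: more than 10% of a cohort with a total symptom score above 40.
- 9.2.4.2: "Any subject experiences type 1 hypersensitivity immediately after receiving the study product".
- 9.2.4.3: any SAE that the investigator judges related to the challenge virus infection.

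Three other places bear on what happens once a rule is met:

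- Section 9.3.2 covers any halting rule that is met after either the initial inoculation or the re-challenge. The consequence it sets is that "the study will not proceed with the remaining enrollment or study challenge without a review by and recommendation from the DSMB".
- Section 11.4.1 says that unexpected or serious events related to the challenge "will be reviewed with the ISM, the DSMB and DMID before the next cohort is challenged".
- Section 9.2.3 says of the symptom-score threshold: "Should this occur we will report the event to the Medical Monitor and stop the study pending DSMB review".

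**The concern.** Section 9.2.4 gives one reason, the short inoculation window, for exempting all three rules from use within a cohort. A short window is a good reason only if the triggering information arrives after the window closes. For an immediate reaction to the product it arrives while other volunteers are still waiting.

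At stake is the safety of healthy volunteers who have no individual benefit from taking part (section 2.3.2). As 9.2.4 is written, mandatory action after an immediate hypersensitivity reaction is deferred until the cohort has been dosed. Whether the rest of the session goes ahead is then left to judgement on the day.

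**Working it through.** There is no stated figure to reproduce. The check compares when each rule can be known with when the sections require action.

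**Step 1. When can each rule be known?**

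| Rule | Information needed | Knowable during inoculation? |
|---|---|---|
| 9.2.4.1 symptom score | Scores on Study Days 1 to 5, from more than 10% of the cohort | No |
| 9.2.4.2 immediate hypersensitivity | One reaction in one volunteer | Yes |
| 9.2.4.3 related SAE | One SAE attributed to the virus infection | Possible, but more likely later |

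For 9.2.4.1, section 8.2.3 says: "The total symptom score will be the sum of the symptom scores for all symptoms on Study Days 1-5". Section 8.2.2 lists eight symptoms, each scored 0 to 3, so the daily maximum is 8 × 3 = 24. A score above 40 therefore cannot be reached on Study Day 1 (24), only from Study Day 2 (48). If the two inoculation days are consecutive (an assumption), Study Day 2 falls after dosing has finished, even for volunteers dosed on the first day. In a cohort of 25 the rule also needs more than 0.10 × 25 = 2.5, so at least 3 volunteers. The 9.2.4 reason holds for this rule.

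For 9.2.4.2 it does not hold. The rule needs one volunteer, and its own wording places the event directly after dosing. It can be acted on before the next volunteer and before a second inoculation day.

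**Step 2. What do the sections require for the rest of the same cohort?**

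- Section 9.2.4 requires review before subsequent challenges and says the rules are not applied during the cohort. Section 11.4.1 places review before the next cohort.
- Section 9.3.2, subject by subject: a challenge is one volunteer's dosing (section 6.2.2 uses the word this way), so volunteers still waiting may not be dosed until the DSMB has reviewed.
- Section 9.3.2, cohort by cohort: a challenge is the whole cohort's event (section 9.2.2.2 uses the word this way), so what remains is the re-challenge and later cohorts. This agrees with 9.2.4 and 11.4.1.

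On the first reading, 9.3.2 requires a stop that 9.2.4 says cannot be made. On the second the sections agree, but no halting rule stops the session. Either way 9.2.4 needs correcting.

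**Step 3. Does other text order a same-session stop?**

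- The instruction to stop in 9.2.3 applies only to the symptom-score rule, which cannot be met during inoculation.
- Rule 9.2.4.3 is tied to the virus infection and may not capture a reaction to the product.
- The scheduled DSMB review in 9.3.2 follows the visit seven days after first inoculation, when the cohort has been dosed.

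**Step 4. Who could be affected?**

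If the volunteer in position k of n reacts, n − k are still waiting. Section 4.2 plans about 25 first challenges in each of the first two years, so the maximum is 25 − 1 = 24. The size of the third cohort is to be adjusted, so its count may differ. This counts people waiting; it is not a risk, because no reaction rate is given.

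**The case against.** The strongest case against the point is that the halting rules only define when DSMB review is compulsory. Nothing in 9.2.4 tells staff to carry on dosing or forbids a pause. The investigator gives every inoculum (6.3), the PI monitors safety during challenges (9.3.3), and DMID, the DSMB, the ISM or the PI can call an ad hoc DSMB meeting (9.3.2). A sensible investigator would stop. The hazard also looks small: stock containing 10% serum at 3.9 × 10⁴ TCID₅₀/mL is diluted to 20–100 TCID₅₀/mL, that is 390-fold (39,000/100) to 1,950-fold (39,000/20), leaving about 0.026% to 0.005% serum (6.1.2, 6.2.1), and total IgE must be below 200 IU/mL (5.2).

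All of this stands as mitigation, and it keeps the point modest. It does not remove it: those safeguards are discretionary, while the only explicit statement on halting during a cohort is that it cannot be done.

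A reader might go further and infer that 9.2.4 and 9.3.2 flatly contradict each other. The documents do not support that. Section 9.3.2 never says that halting applies within a cohort, its paragraph on scheduled review is organised by cohort, and its wording can be reconciled with 9.2.4 and 11.4.1. What can be shown is ambiguity.

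**Conclusion.** The point holds as a safety-wording defect that should be corrected. The stated reason is valid for 9.2.4.1, invalid for 9.2.4.2, and only partly apt for 9.2.4.3, where an event before dosing is complete is less likely. Section 9.3.2 is ambiguous, and neither reading leaves 9.2.4 satisfactory.

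The probability of a trigger appears low but cannot be estimated from the documents. The planned analyses are unaffected unless one occurs. The conclusion rests on the protocol alone: the Manual of Procedures and DSMB charter were not available, and a stop instruction in either would reduce this to a matter of alignment.

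**What to change.** 1. In 9.2.4, limit the sentence about halting during the cohort to the symptom-score rule, 9.2.4.1.
2. State that a 9.2.4.2 event, or a related SAE before inoculation is complete, immediately pauses all further inoculation, including the rest of the same cohort. The ISM assesses at once, and dosing resumes only after an expedited ad hoc DSMB review under 9.3.2. At re-challenge the pause should cover both virus pools, because they share the same medium and diluent (6.1.2, 6.2.1); the DSMB can then release one or both.
3. Reword 9.3.2 and 11.4.1 to match, making explicit that the pause reaches volunteers still waiting in the same cohort.

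Unless triggered, this costs protocol wording only. If triggered, the rest of that cohort's challenges, up to about 24 in a cohort of 25, may be delayed or lost within the school calendar (4.2, 5.1). Restarting on a later day needs a fresh dilution (6.1.3) and a repeat of the pregnancy screen and the nasal lavage for respiratory virus PCR (7.3.1, 7.4.1). At re-challenge, delay would also separate the Week 15 T-cell sample, which feeds the primary outcome measure, from the inoculation, or require another 105 mL draw (7.3.7). Section 4.2 lets the final cohort make up attrition in the first two, but no later cohort can make up its own losses. An ISM-only release would be quicker, but it would leave out the DSMB review that 9.2.4 already requires before subsequent challenges.
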